Day 27 is the last possible day that symptom alleviation can be achieved (definition includes data from the subsequent day) and Day 28 is the last day participants report their daily signs and symptoms.

The time to sustained symptom alleviation for the purpose of this study is defined as:

- For a participant with sustained symptom alleviation, time to event will be calculated as (First Event Date) – (First Dose Date) +1.
- For a participant that either completes Day 28 of the study or discontinues from the study before Day 28 without sustained symptom alleviation(censored), censoring date will be at the last date on which symptom alleviation is assessed, and time will be calculated as (Censoring Date) – (First Dose Date) +1 or Day 27 whichever occurs first.

Participants who are hospitalized for the treatment of COVID-19 or die from any cause during the 28-day period will be classified as not achieving sustained symptom alleviation and will be censored at day 27.

Cox proportional hazard model analyses will be used for time to sustained symptom alleviation in mITT analysis set. Cox proportional hazard model will include treatment, geographic region and potential covariates as appropriate. The treatment group comparison

will be presented as the estimate of the hazard ratio, 95% CI and p-value. In addition, time to sustained symptom alleviation will be summarized graphically using Kaplan-Meier plots for each of the treatment groups in mITT analysis set.

Similar analyses for time to sustained symptom alleviation will also be performed in the mITT1 analysis set.

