1. VERSION HISTORY

Table 1. Summary of Changes

Version/ Date	Associated Protocol Amendment	Rationale	Specific Changes
Version 1/ 30 Sep 2022	Protocol amendment 1 16 Sep 2022	Original SAP	N/A
Version 2/ 12 Oct 2023	Protocol amendment 4 29 Jun 2023	Protocol amendment 4 changes, regulatory feedback and other clarification	
 • Updated the analysis populations in Section 2.2, 4, 5.1, 6.1, 6.2 and 6.3 for primary, secondary and relevant tertiary/exploratory objective/estimand/endpoints to align with protocol change. • Updated Section 2.4 sample size to align with protocol change. • Added site exclusion for efficacy related analysis sets in Section 4. • Added secondary analyses for primary and secondary endpoints in Section 6.1 and 6.2 to align with protocol change. Updated the multiplicity adjustment accordingly in Section 5.1. • Removed the analysis details for infectious titer by TCID50 and by virus recovery in Section 3.4, 4 and 6.3. These analyses will be specified in virology analysis plan. • Add analysis details for potential covariates in Section 6.2.1 and 6.2.2 • Added analysis details for time to sustained NP Swab SARS-CoV-2 RNA below the LLOQ in Section 6.3.5. • Added two alternative definitions/analyses of rebound in Section 6.3.6. • Added other analysis for the concordance of rapid antigen and RT-PCR test results in Section 6.3.12. • Added additional subgroups analyses in Section 6.4. • Updated Appendix 1 to align with the analysis updates/changes in SAP main body. • Updated the handling of multiple measurements on the same day for lab data in Appendix 2.1.

Table 1. Summary of Changes

Version/ Date	Associated Protocol Amendment	Rationale	Specific Changes
			
 Added Appendix 4 for Participant-Reported COVID-19-Related Signs and Symptoms Editorial change throughout the document.

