6.1.1. Main Analysis

The primary analysis for mean change in SARS-CoV-2 RNA level from baseline will be performed using a MMRM. The analysis will include the fixed effects of treatment, geographic region, baseline viral RNA level, visit, and treatment-by-visit interaction. An unstructured (co)variance structure will be used to model the within-participant variability. The LS means and treatment difference for each visit will be calculated and presented with their corresponding 95% CIs. The primary comparison for treatment effect will be the difference in LS means and 95% CI at Day 5. The primary analysis will be performed using mITT analysis set.

The secondary analysis for primary endpoint will be performed using the mITT1 analysis set. In the analysis, samples with result “<LLOQ” will be imputed as $1.7 \log_{10}$ copies/mL, and samples with result “undetectable” will be imputed as $0.0 \log_{10}$ copies/mL.

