6.2. Secondary Endpoint(s)

6.2.1. Time to 2 Consecutive Negative Rapid Antigen Test Results Obtained at least 24(-2)h Apart through Day 28

The event of 2 consecutive negative rapid antigen test results obtained at least 24(-2)h apart through Day 28 is defined as achieving two consecutive non-missing rapid antigen test with negative results through Day 28, where the two tests are at least 22 hours and at most 7 days apart. For the event of 2 consecutive negative rapid antigen test results obtained at least 24(-2)h apart through Day 28, the date of the first negative rapid antigen test result will be considered the First Event Date.

Time to 2 consecutive negative rapid antigen test results obtained at least 24(-2)h apart for the purpose of this study is defined as:

- For a participant achieving the event, time to event will be calculated as (First Event Date) – (First Dose Date) +1.
- For a participant not achieving the event (censored), censoring date will be at the last date of rapid antigen test measurement, and time will be calculated as (Censoring Date) – (First Dose Date) +1 or Day 27 whichever occurs first (Day 27 is the last possible day to achieve 2 consecutive negative rapid antigen test results obtained at least 24(-2)h apart through Day 28).

Participants who are hospitalized for the treatment of COVID-19 or die from any cause during the 28-day period will be classified as not achieving the event and will be censored at Day 27.

Cox proportional hazard model analyses will be used for time to 2 consecutive negative rapid antigen test results obtained at least 24(-2)h apart in mITT analysis set. Cox proportional hazard model will include treatment, geographic region, baseline viral load (< 4 or ≥ 4) and time since the last vaccination (≤ 6 months, > 6 months or unvaccinated) as appropriate. The treatment group comparison will be presented as the estimate of the hazard ratio, 95% CI and p-value. In addition, time to 2 consecutive negative rapid antigen test results obtained at least 24(-2)h apart will be summarized graphically using Kaplan-Meier plots for each of the treatment groups in mITT analysis set.

The log-rank test will be performed as additional analysis to compare the treatment group using mITT analysis set.

Similar analyses for time to 2 consecutive negative rapid antigen test results obtained at least 24(-2)h apart will also be performed in the mITT1 analysis set.

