6.2.2. Time (days) to Sustained Alleviation of All Targeted Signs and Symptoms through Day 28

Sustained alleviation of all targeted COVID-19 signs/symptoms is defined as the event occurring on the first of 2 consecutive days when all symptoms scored as moderate or severe at study entry are scored as mild or absent AND all symptoms scored mild or absent at study entry are scored as absent. The first day of the 2 consecutive-day period will be considered the First Event Date.

For symptoms with no reported severity in baseline, the symptom will have to be absent in order to be counted as sustained alleviated (missing severity at baseline will be treated as mild).

Day 27 is the last possible day that symptom alleviation can be achieved (definition includes data from the subsequent day) and Day 28 is the last day participants report their daily signs and symptoms.

The time to sustained symptom alleviation for the purpose of this study is defined as:

- For a participant with sustained symptom alleviation, time to event will be calculated as (First Event Date) – (First Dose Date) +1.
- For a participant that either completes Day 28 of the study or discontinues from the study before Day 28 without sustained symptom alleviation(censored), censoring date will be at the last date on which symptom alleviation is assessed, and time will be calculated as (Censoring Date) – (First Dose Date) +1 or Day 27 whichever occurs first.

Participants who are hospitalized for the treatment of COVID-19 or die from any cause during the 28-day period will be classified as not achieving sustained symptom alleviation and will be censored at Day 27.

Cox proportional hazard model analyses will be used for time to sustained symptom alleviation in mITT analysis set. Cox proportional hazard model will include treatment, geographic region baseline viral load (< 4 or \geq 4) and time since the last vaccination (\leq 6 months, $>$ 6 months or unvaccinated) as appropriate. The treatment group comparison will be presented as the estimate of the hazard ratio, 95% CI and p-value. In addition, time to sustained symptom alleviation will be summarized graphically using Kaplan-Meier plots for each of the treatment groups in mITT analysis set.

Similar analyses for time to sustained symptom alleviation will also be performed in the mITT1 analysis set.

6.2.3. Incidence of Treatment Emergent Adverse Events (TEAEs); Incidence of SAEs and AEs Leading to Discontinuation

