6.3.12. Other analyses

For the rapid antigen test and NP swab SARS-CoV-2 RNA/RT-PCR test that are collected on the same study day, the concordance analysis will be performed at each visit, across post-baseline visits and across all visits for the each treatment group and overall/combined treatment group in mITT1 analysis set. Kappa statistic will be provided as a measurement of agreement between rapid antigen test and RT-PCR for across post-baseline visits and across all visits.

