6.4. Subset Analyses

Subgroup analyses of the primary endpoint (if data permitted) will include:

- Age group (<18, 18 to <60, ≥ 60) and (<65, ≥ 65);
- Gender;
- Race;
- Ethnicity;
- BMI category (<25, 25 to <30, ≥ 30);
- Baseline viral load ($<7 \log_{10}$ copies/mL, $\geq 7 \log_{10}$ copies/mL; $<4 \log_{10}$ copies/mL, $\geq 4 \log_{10}$ copies/mL);
- Geographic region (US, Ex-US) .

A forest plot will display confidence intervals across subgroups.

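### The secondary Cox models use baseline viral load only as <4 versus ≥4; entering the log10 level would usually give somewhat more power for antigen clearance if RNA has a graded effect

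*SAP*

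**What the plan says.** For time to two consecutive negative antigen tests, SAP 6.2.1 lists treatment with "geographic region, baseline viral load (< 4 or ≥ 4) and time since the last vaccination" as the Cox terms, qualified by an as-appropriate clause. SAP 6.2.2, on sustained symptom alleviation, has the same terms: "Cox proportional hazard model will include treatment, geographic region baseline viral load", again split at 4. No unit is given in either place. Log10 copies/mL is inferred from the subgroup list in SAP 6.4, which splits baseline load at 4 and also at 7.

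The protocol left the covariates open (9.3.3.1 and 9.3.3.2): "Cox proportional hazard model will include treatment, geographic region and potential covariates as appropriate". SAP version 2 filled them in, and its change log says only "Add analysis details for potential covariates in Section 6.2.1 and 6.2.2". The stated rationale for version 2 mentions regulatory feedback in general and does not tie it to this cut.

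The primary model handles the same variable differently (SAP 6.1.1): "The analysis will include the fixed effects of treatment, geographic region, baseline viral RNA level, visit, and treatment-by-visit interaction", with no categories named. By definition, every mITT participant has a baseline value of at least 2.0 log10 copies/mL (SAP 4). Both Cox endpoints are tested in mITT by Hochberg within the overall 0.05 (SAP 5.1), and the hazard ratio is the named estimand (SAP 2.2.2).

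**The concern.** The level is available for everyone in the tested population, yet the Cox models treat 4.1 and 8 as the same value. The split at 7 in SAP 6.4 shows that the plan itself expects variation above 4.

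The Cox hazard ratio is non-collapsible. If prognostic variation is left out, the model estimates a treatment hazard ratio closer to 1, while the standard error hardly changes. Power therefore falls. A graded RNA effect is plausible for antigen clearance, since the plan expects antigen and RNA results to be related closely enough to measure their agreement (SAP 6.3.12): "Kappa statistic will be provided as a measurement of agreement between rapid antigen test and RT-PCR". That is a reason to think of it, not evidence of prognosis. At stake is some efficiency on a key secondary test, and clarity about which hazard ratio is reported.

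**Working it through.** **The plan's own figure.** The documents give a power calculation for the primary endpoint only. Control n = (1.960 + 1.282)² × 1.8² × (1 + 1/2) / 0.7² = 10.51 × 3.24 × 1.5 / 0.49 = 104.2, so 105, with 210 on active: 315, as stated, with power 90.2%. Then 315 / 0.90 / 0.85 = 411.8, against 411 stated. Neither document gives a power, hazard ratio or event count for the Cox endpoints.

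**Inputs from the documents.** n = 411 × 0.90 = 370 in mITT; 2:1 allocation; two-sided 0.05; last event day 27. The only RNA figures for rebound patients are from a series of 7: median 6.1, range 4.2 to 7.3 (Protocol 2.1).

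**Share below 4.** None of the 7 was below 4. The exact upper limit is 1 − 0.025^(1/7) = 41%, so the series does not settle it. The plan's 10% RNA-negative assumption points to lower values: a normal with mean 3.8 and SD 1.4 has 9.9% below 2.0, and (0.557 − 0.099) / (1 − 0.099) = 51% of the remainder below 4. The checks therefore run from 4% to about 50%.

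**What the cut retains.** For a normal variable the two-level term keeps φ(z)² / [Φ(z)(1 − Φ(z))] of the variance. With mean 6.1 and SD 1.2, z = (4 − 6.1)/1.2 = −1.75, giving 0.0863² / (0.040 × 0.960) = 19%. With mean 5.3 and SD 1.4, truncated at 2.0, it keeps 44%.

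**Simulated power, cut versus continuous (%).** Assumed, not in the documents: a log-linear RNA effect with the hazard ratio per log10 shown. Set I: treatment HR 1.40, placebo median 7 days. Set II: treatment HR 1.45, placebo median 8 days, about 10% dropout.

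| Set | Mean, SD | Below 4 | 0.9 per log10 | 0.8 | 0.7 |
|---|---|---|---|---|---|
| I | 6.1, 1.2 | 4% | 82 v 83 | 78 v 82 | 75 v 83 |
| I | 5.3, 1.4 | 17% | 83 v 83 | 80 v 83 | 73 v 82 |
| I | 3.8, 1.4 | 51% | 83.4 v 83.3 | 83.1 v 84.9 | 81.2 v 83.8 |
| II | 6.1, 1.5 | 8% | 87.7 v 89.0 | 83.9 v 87.7 | 78.4 v 87.7 |
| II | 5.0, 1.8 | 25% | 87.5 v 88.3 | 84.5 v 87.9 | 79.6 v 86.9 |
| II | 4.0, 1.8 | 42% | 87.3 v 88.1 | 85.3 v 87.2 | 82.1 v 85.6 |

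Replicates: 4000 for the first two rows (unrounded paired losses 0.9/3.9/7.9 and 0.7/3.5/8.2 points), 1000 for the third, 1500 for set II. Rounded, the losses are about 0 to 1.5, 2 to 4, and 3 to 8 points. The exception is 87.7 − 78.4 = 9.3 at 0.7 in the fourth row.

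**Mechanism by hand** (first row, 0.7 per log10). Mean HR is 1.35 with the cut and 1.40 with the level; the standard errors are 0.1167 and 0.1169. ln 1.40 / 0.1169 = 2.88, so power is about Φ(2.88 − 1.96) = 82%. ln 1.35 / 0.1167 = 2.57, so Φ(0.61) = 73%. These are close to the simulated 83% and 75%. The loss comes from the smaller estimate, not from precision.

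**Where the loss vanishes or reverses** (set I, first two rows' distributions).
- RNA not prognostic: 83 v 83 and 83 v 82.
- Effect flat above 6, slope 0.8 below: 83 v 84 and 81 v 81.
- True effect a step exactly at 4: the continuous term loses 1.7 to 2.1 and 2.6 to 6.7 points.

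**Type I error.** Set I: 4.5 to 5.4% with the cut, 4.8 to 5.1% with the level. Set II: 5.7% and 5.2 to 5.5%.

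**mITT1** (n = 411, 10% negative, slope 0.8). The continuous term gains 2 to 3 points whether negatives are set to 0.0 or to 1.7.

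**The case against.** The strongest reply is that this is an efficiency preference. Nothing in the documents shows that baseline RNA is prognostic for either endpoint. The concordance analysis in SAP 6.3.12 compares same-day results, and the split at 7 in SAP 6.4 is a subgroup for the RNA endpoint. The functional form is unknown, and a step at 4 would favour the cut. The MMRM is an imperfect precedent, because there baseline is a component of the outcome. The cut also has practical merits: it matches a prespecified subgroup boundary, and it works unchanged in mITT1, where imputed values of 1.7 and 0.0 both fall below 4. Regulatory feedback not reproduced in the SAP may lie behind it. Baseline distributions in line with the plan's 10% RNA-negative assumption shrink the loss to about 0 to 3 points.

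Most of this stands, and it is why the size is conditional and the range wide. It does not remove the point: under a graded effect the continuous term gains at 0.8 and 0.7 in every distribution tried, including those with 42% and 51% below 4. The step at 4 has no support in the documents either. The cut also remains better than no RNA term (78.4% against 75.4% in the fourth row at 0.7).

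A reader might infer that the cut biases the treatment effect or invalidates the tests. The documents do not support that. The estimands in SAP 2.2.2 name no conditioning covariates, so the two hazard ratios are different conditional quantities and neither is the wrong target. The shift from 1.40 to 1.35 is ln(1.40/1.35) / 0.117 = 0.3 standard errors. A reader might also infer a loss of about 8 points on both endpoints. That needs a strong graded effect and few participants below 4, and no graded effect is claimed for symptom alleviation.

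**Conclusion.** The point holds as a low-cost improvement, not as an error. The two-level term is valid, keeps type I error near 5%, and misses no stated power target. If baseline RNA acts in a graded way on antigen clearance, the cut gives a hazard ratio nearer 1 and costs roughly 0 to 1.5, 2 to 4 or 3 to 8 power points at 0.9, 0.8 or 0.7 per log10. Which figure applies depends on the share of participants below 4, the spread of baseline RNA and the treatment effect, none of which the documents fix. Whatever the power effect, the unit and the reason for 4 are missing where the models are specified. Confidence is medium, because the prognostic strength, treatment hazard ratio and event rate are all assumed.

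**What to change.** Before unblinding, replace the <4/≥4 term in the mITT Cox model of SAP 6.2.1 with continuous baseline log10 NP RNA (copies/mL), and do the same in 6.2.2 for consistency. Keep the <4/≥4 model as a sensitivity analysis with its unit stated. Say that the reported hazard ratio is conditional on continuous baseline RNA and so differs from the one conditional on the cut.

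For mITT1, either apply the imputation rule of SAP 6.1.1 to the covariate (1.7 for results below LLOQ, 0.0 for undetectable) or keep the categorical term there, where imputed values have no leverage. If the cut stays as the main term, give its unit and the reason for 4.

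Cost: SAP wording, one model term and one extra run per endpoint, with no new data or participants. Downsides: an assumed linear effect, with the 2 to 7 point loss if the truth is a step at 4, and a changed conditional hazard ratio that must be disclosed.

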6.3. Tertiary/Exploratory Endpoints

6.3.1. Proportion of Participants with SARS-CoV-2 RNA in NP Swab below the LLOQ on Days 3, 5, 10, 15, 21, 28, and 34

The number and proportion of participants with SARS-CoV-2 RNA level in NP swabs $<2.0 \log_{10}$ copies/mL at 3, 5, 10, 15, 21, 28, and 34 will be summarized by treatment group. The analysis will be done using mITT analysis set.

6.3.2. Proportion of Participants with Sustained NP Swab SARS-CoV-2 RNA below the LLOQ (defined as $<2.0 \log_{10}$ copies/mL) from Day 5 through Day 34

The number and proportion of participants with sustained NP swab SARS-CoV-2 RNA $<$ LLOQ (defined as $<2.0 \log_{10}$ copies/mL) from Day 5 through Day 34 will be summarized by treatment group using mITT analysis set.

Sustained SARS-CoV-2 RNA below the LLOQ from Day 5 through Day 34 is defined as having all non-missing measurements from Day 5 to Day 34 below the LLOQ and no more than 3 visits with missing SARS-CoV-2 RNA levels (scheduled collection on Days 5, 10, 15, 21, 28 and 34).

6.3.3. Proportion of Participants with SARS-CoV-2 RNA in NP Swabs below the LLOQ (defined as $<2.0 \log_{10}$ copies/mL) on both Days 5 and 10

The number and proportion of participants with SARS-CoV-2 RNA in NP swabs below the LLOQ (defined as $<2.0 \log_{10}$ copies/mL) on both Days 5 and 10 will be summarized by treatment group. The analysis will be done using mITT analysis set.

6.3.4. Change in SARS-CoV-2 RNA Level in NP Swabs from Baseline to Days 3, 10, 15, 21, 28, and 34

Change in SARS-CoV-2 RNA level in NP swabs from baseline to Days 3, 10, 15, 21, 28, and 34 will be analyzed similarly to the primary endpoint using MMRM model in the mITT analysis set. The LS means and treatment difference for each visit will be calculated and presented with their corresponding 95% CIs.

6.3.5. Time to Sustained NP Swab SARS-CoV-2 RNA below the LLOQ (defined as $<2.0 \log_{10}$ copies/mL) and Remains below the LLOQ through Day 34 for Participants with NP Swab SARS-CoV-2 RNA Greater than or Equal to the LLOQ at Baseline

Time to sustained NP swab SARS-CoV-2 RNA below the LLOQ (defined as $<2.0 \log_{10}$ copies/mL) and remains below the LLOQ through Day 34 will be summarized graphically using Kaplan-Meier plots for each of the treatment groups. The analyses will be done similarly as in Section 6.2.2 using the mITT analysis set, which includes participants with baseline viral load \geq LLOQ.

Sustained is defined as NP swab SARS-CoV-2 RNA level not $\geq 2.0 \log_{10}$ copies/mL at any study visit (through Day 34) following the first study visit where the participant's NP swab SARS-CoV-2 RNA $<$ LLOQ.

Let t represent the study day t between Day 5 and 28 visit inclusive for which there is a measurement of SARS-CoV-2 RNA level.

Then a sustained event will correspond to the first possible value of t to satisfy the following criteria:

- a) The Day t SARS-CoV-2 RNA level is $<$ LLOQ
- b) At least one SARS-CoV-2 RNA measurement is $<$ LLOQ after Day t
- c) All available (non-missing) SARS-CoV-2 RNA measurements between Day t and Day 34 visit are $<$ LLOQ
- d) No more than 50% missingness between Day t and Day 34 are missing.

There are limitations to the timing of the first event date as NP viral RNA is generally only captured at scheduled visits during the study.

The Day 28 visit is the last possible day the sustained NP swab SARS-CoV-2 RNA $<$ LLOQ can be achieved.

The time to the sustained event is defined as:

- For a participant with sustained event at Day t , the First Event Date is the date of the Day t measurement, and time to event will be calculated as (First Event Date) – (First Dose Date) +1.
- For a participant for which no possible value of $t \leq$ the Day 28 visit satisfies the criteria for a sustained event (censored), censoring date will be the date of the last available protocol-specified SARS-CoV-2 RNA measurement other than Day 34 visit, and time will be calculated as (Censoring Date) – (First Dose Date) +1.

6.3.6. Rebound in SARS-CoV-2 RNA Level in NP Swabs at Follow-up ie, Any Study Visit from Day 10 to through Day 34, Defined as a Half (0.5) Log₁₀ Copies/mL Increase or Greater in SARS-CoV-2 RNA Level Relative to SARS-CoV-2 RNA Level on Day 5 and with a Follow-up Viral RNA Level ≥ 2.5 Log₁₀ Copies/mL

The number and proportion of participants with rebound in SARS-CoV-2 RNA level in NP swabs up at follow-up will be summarized by treatment group. The analyses will be done using mITT analysis set.

In addition, two alternative definitions of rebound will also be evaluated:

- Rebound that is defined as: SARS-CoV-2 RNA level in NP swabs at follow up (ie, any study visit after Day 5 through Day 34) that is defined as a half (0.5) log₁₀ copies/mL increase or greater in SARS-CoV-2 RNA level relative to SARS-CoV-2 RNA level on Day 5, with a follow-up viral RNA level ≥ 3.0 log₁₀ copies/mL.
- Rebound that is defined as: SARS-CoV-2 RNA level in NP swabs at follow up (ie, any study visit after Day 5 through Day 28) that is defined as a half (0.5) log₁₀ copies/mL increase or greater in SARS-CoV-2 RNA level relative to SARS-CoV-2 RNA level based on Day 5, with a follow-up viral RNA level ≥ 3.0 log₁₀ copies/mL.

The rebound analyses will be restricted to those participants with non-missing SARS-CoV-2 RNA measurement on DAY 5 and at least one non-missing measurement among after Day 5 visit through the Day 34 visit (or through the Day 28 visit for the second alternative definition of rebound analysis).

